7.2.1 General considerations

The following populations are planned in this trial for main efficacy and safety analyses:

Treated Set (TS)

This patient set includes all patients who were randomized and received at least one dose of study drug. It will be the main analysis set for presentation of efficacy and safety. Patients will be analyzed according to the actual treatment.

Per-Protocol Set (PPS)

This patient set includes all patients in the safety analysis set who adhered to the CTP without any Important Protocol Deviations (IPDs) potentially affecting the study outcome which lead to exclusion from the PPS. This set will be used for sensitivity analysis on the primary endpoint.

Important deviations of the protocol will include deviations of the key inclusion and exclusion criteria, incorrect medications taken, concomitant use of restricted medications and any other deviations of the protocol deemed important by the study team. All decisions concerning important protocol deviations will be made prior to un-blinding of the database for the final trial analysis.

Further analysis sets, e.g. for the biomarker assessments, will be defined in the Trial Statistical Analysis Plan (TSAP).

Standard statistical parameters (number of non-missing values, mean, standard deviation (SD), median, quartiles, minimum and maximum) or frequency tables (including patient frequencies and percentages) will be calculated where appropriate.

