7.2.2 Primary endpoint analyses

The difference in percent change from baseline in total abscess and inflammatory nodule at Week 12 between spesolimab and placebo is the primary endpoint of this trial. All on-treatment data are planned to be included into analysis but any data after use of any rescue therapy will be censored in line with the primary objective to estimate the treatment effect in treated patients assuming they do not receive rescue therapy (primary estimand). To account for the repeated nature of the data, the primary analysis is a restricted maximum likelihood (REML) based approach using a mixed model with repeated measurements (MMRM) comparing the adjusted relevant difference between the two arms.

The analysis will include the fixed categorical effects of treatment at each visit, stratum and the fixed continuous effect of baseline at each visit. Visit will be treated as the repeated measure with an unstructured covariance structure to model the within-patient measurements.

The statistical model will be as follows:

$$y_{ijkm} = \beta_j S_i + \tau_{jk} + \Phi_m + e_{ij}$$

With

- y_{ijkm} response variable for patient i in stratum m at visit j receiving treatment k
- S_i baseline measurement of patient i , $i=1,2,\dots$
- β_j coefficient of baseline effect at visit j
- τ_{jk} effect of treatment k at visit j , $j=3,\dots,9$ and $k=1, 2$
- Φ_m effect of stratum m , $m=1,2$
- e_{ij} random error associated with visit j of patient i .

Errors are independent between patients with $e_{ij} \sim N_z(0, \Sigma)$ and Σ is an unstructured covariance matrix.

The Kenward-Roger approximation will be used to estimate denominator degrees of freedom and adjust standard errors. Due to the exploratory character of this trial no significance test will be done. However, least-squares means (adjusted means) of each arm as well as adjusted treatment differences will be provided together with two-sided 95 %-confidence intervals for each time point.

The patients will be analysed according to the stratum to which they belong (regardless of any mis-assignment to treatment based on identification of the wrong stratum), as such an error occurs before randomization and is therefore consistent with regulatory guidance. Procedures to follow if the analysis fails to converge will be described in the TSAP.

Secondary analysis of the primary endpoint will include:

[figure not shown]

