6.2 IMPORTANT PROTOCOL DEVIATIONS

Data discrepancies and deviations from the CTP will be identified for all patients in the database (i.e., enrolled patients). Consistency check listings (for identification of deviations of time windows) and a list of protocol deviations will be provided to be discussed at the RPM/DBLM. At this meeting, it will be decided whether a discrepant data value can be used in analyses or whether it must be queried in the clinical database. Each protocol deviation must be assessed to determine whether it is an important Protocol Deviation (iPD). These categories are described below in order to ensure that those iPD which lead to exclusion from the PPS are suitably documented before unblinding and locking of data.

For definition of iPDs, and for the process of identification of these, refer to the BI reference document "Identify and Manage Important Protocol Deviations (iPD)". (8)

If any patients fulfil the iPD categories, then they are to be summarized and will be captured in the RPM/DBLM minutes via an accompanying Excel spreadsheet (3). The following table contains the categories which are considered to be iPDs in this trial. If the data show other iPDs, for example, based on monitor visits to the site(s), then this table will be supplemented accordingly by the time of the RPM/DBLM. Not all iPDs will lead to exclusion from analysis sets. iPDs leading to exclusion from analysis sets are indicated as such in [Table 6.2: 1](#).

iPDs will be summarized and listed for the randomized set.

Table 6.2: 1 Important protocol deviations

Category/ Code	Description	Comments	Excluded from¹
A	Entrance criteria violated		
A1	Inclusion criteria not met		
A1.01	Male or female adult patients, 18 years of age or older LABEL: Age not met	IC01 Also require programmatic check	PPS

Proprietary confidential information © 2021 Boehringer Ingelheim International GmbH or one or more of its affiliated companies

A1.02	Moderate to severe HS, based on IHS4 criteria, for at least 1 year prior to the baseline visit LABEL: medical history of HS not met based on IHS4	IC03	PPS
A1.03	HS lesions in at least 2 distinct anatomic areas LABEL: HS lesions in less than 2 anatomic areas	IC04	PPS
A1.04	Biologic naïve or TNFi-failure for HS LABEL: Not Biologic naïve or TNFi-failure for HS	IC05	PPS

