A2.19	Previous enrolment in this trial except for patients re-screened. LABEL: Previous enrolment in this trial except for patients re-screened	EC19	PPS
B	Informed consent		
B1	Informed consent not available LABEL: No IC form	IC02 Date of informed consent missing or no signature on patient's "Declaration of Informed Consent" In this case: Patient's data will not be used at all.	All
B2	Informed consent too late LABEL: IC too late.	IC02 Informed consent date was after Visit 1	None
C	Trial medication and randomisation		
C1	Incorrect trial medication		
C1.01	Study drug medication not taken at all LABEL: Study drug medication not taken at all.		PPS, SAF
C1.02#	Patient skipped an intermediate dose without proper reason LABEL: Patient skipped an intermediate dose without proper reason.	Patient missing a dose at an intermediate visit without proper reason when dose at a later scheduled visit has been taken. Decision based on medical judgment.	PPS

Proprietary confidential information © 2021 Boehringer Ingelheim International GmbH or one or more of its affiliated companies

C1.03#	Patient skipped an intermediate dose due to COVID 19 LABEL: Patient skipped an intermediate dose due to COVID 19	Patient missing a dose at an intermediate visit when dose at a later scheduled visit has been taken due to covid-19 Decision based on medical judgment.	PPS
C2	Incorrect Dosing		
C2.01	Incorrect medication received prior to Week 12 LABEL: Incorrect dose received prior to Week 12	Randomized patient who received or miss one or more incorrect syringes of treatment not as planned at any scheduled visit prior to Week 12 Can only be finally judged after DBL since unblinding information is required	PPS
C3	Randomization not followed		
C3.01	Treated without randomisation LABEL: Treated without randomisation.	Patient treated according to eCRF, but not randomised according to IVRS.	RS, SAF, PPS
C3.02	Randomization order of stratification not followed LABEL: Stratification error	Stratification error regarding TNFi naïve and TNFi-failure Programming check and manual review after DBL	PPS
C4	Medication code broken		
C4.01	Medication code broken before week 12 inappropriately LABEL: Code broken early without valid reason.	Medication code was broken prior to DBL for no valid reason. Final decision at the DBL meeting based on medical judgment.	PPS
D	Concomitant medication		
D1	Previous medication		

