6.3 SUBJECT SETS ANALYSED

The following analysis sets will be defined for this trial:

Enrolled Set (ES)

This patient set includes all patients who signed informed consent. It will be used for analyses of patient disposition.

Randomized Set (RS):

This patient set includes all randomized patients. Treatment assignment will be as randomized.

Safety Analysis Set (SAF):

This patient set includes all patients who were randomized and received at least one dose of study drug. This is the main analysis set for efficacy and safety. Patients will be analyzed according to the actual treatment received.

Per-Protocol Set (PPS):

This patient set includes all patients in the randomized set who adhered to the CTP without any iPDs which are flagged for exclusion from the PPS in the table above. The PPS will be used for sensitivity analysis on the primary endpoint.

The discussion of all exceptional cases and problems and the decisions on the allocation of patients to populations will be made at latest at the RPM/DBLM.

Handling of Treatment Misallocations in Analysis Sets

If a patient is randomized but not treated, they will not be reported under their randomized treatment group for efficacy and safety analysis according to PPS, and SAF.

If a subject is treated but not randomized, they will be excluded from the efficacy analysis and safety analysis by definition. However, subjects under such circumstances will be described in the final clinical trial report.

If a subject is randomized but takes incorrect treatment during the study, then:

- For efficacy and safety analyses using the SAF which are based on actual treatment:
 - If a subject is planned to receive administration of Spesolimab (randomized to Speso), then they will be reported under the Spesolimab group if the subject receives at least 1 vial of randomized Spesolimab.
 - If a subject is planned to receive placebo treatment, then they will be reported under the placebo arm if they are treated and receive no vial of randomized Spesolimab. If the subject receives ≥ 1 vial of randomized Spesolimab, then the patient will be handled differently for efficacy analysis and safety analysis. It will keep as placebo for efficacy reporting. For safety, then the patient will be reported as treated with Spesolimab treatment group.

Proprietary confidential information © 2021 Boehringer Ingelheim International GmbH or one or more of its affiliated companies

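### Stratification errors (C3.02), which exclude patients from the PPS, are reviewed after database lock against the plan's own rules, although the review needs no treatment code

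*SAP*

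**What the plan says.** SAP Table 6.2:1 lists C3.02 as a stratification error between TNFi-naive and TNFi-failure, with the PPS in the exclusion column. The comment on timing is "Programming check and manual review after DBL".

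The general rules point the other way:

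- SAP 6.2 describes the iPD categories so that "those iPD which lead to exclusion from the PPS are suitably documented before unblinding and locking of data".
- SAP 6.3 states that "the decisions on the allocation of patients to populations will be made at latest at the RPM/DBLM".
- Protocol 7.2.1 states that "All decisions concerning important protocol deviations will be made prior to un-blinding of the database for the final trial analysis".

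One other row of the table, C2.01 (incorrect medication), is also left until after lock, but it gives a reason: "Can only be finally judged after DBL since unblinding information is required". Other rows that call for judgement stay at the meeting. C4.01 is decided at the database lock meeting, and D2.01 to D2.03 are assessed at the MQRM/RPM/DBLM.

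On the use of stratum, Protocol 7.2.2 says "The patients will be analysed according to the stratum to which they belong (regardless of any mis-assignment to treatment". SAP 7.4.1 includes stratum as an effect in the primary MMRM.

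**The concern.** A PPS exclusion is credible when it is fixed by people who cannot know the arm. C3.02 is scheduled later than the plan's own deadline for such exclusions. Under Protocol 4.1.5.1 and SAP 8, if the primary and final analyses are separate, treatment is released to the trial and project teams at the primary-analysis lock. If they are combined, release follows the single lock. In neither case do the documents reserve a blinded period after lock in which this review could take place.

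At stake is the independence of the per-protocol sensitivity analysis of the primary endpoint. There is also a possible knock-on effect: deciding that a patient was stratified wrongly implies deciding the true stratum. Under Protocol 7.2.2, the true stratum is the one that should enter the primary model.

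**Working it through.** **Step 1: timing, rule by rule.**

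| Source | Subject | Deadline |
|---|---|---|
| SAP 6.2, text | iPDs that exclude from the PPS | before unblinding and lock |
| SAP 6.3 | allocation to analysis sets | at latest the RPM/DBLM |
| Protocol 7.2.1 | all iPD decisions | before unblinding for the final analysis |
| SAP Table 6.2:1, C2.01 | wrong medication | after lock; needs treatment information |
| SAP Table 6.2:1, C3.02 | stratification error | after lock; no reason given |

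C3.02 conflicts with SAP 6.2 and 6.3 simply by falling after lock. That conflict does not depend on whether the reviewers hold the codes.

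**Step 2: is the treatment code needed?** The check compares two items. One is the stratum used by the IRT at randomization (Protocol 4.1.3 and 7.4). The other is the history of HS and its previous treatment, recorded in the eCRF at screening (Protocol 6.2.1). Neither reveals the arm. The row's title mentions randomization order, but its comment defines the error as TNFi-naive against TNFi-failure, so the randomization list is not required.

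**Step 3: the plan's own figure, as a check on the inputs.** Protocol 7.5 assumes SD 45 in each arm, 30 and 15 patients, changes of -62% and -20% (a difference of 42 points), and a criterion of at least 30 points.

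- SE = 45 × √(1/30 + 1/15) = 14.23 points.
- P(observed difference ≥ 30) = Φ((42 − 30)/14.23) = Φ(0.843) = 80.05%, against 80.1% stated.
- A 10,000-run gamma simulation, shifted to start at -100% (an assumption), gives 80.4%.
- By the normal formula, all eleven rows of Table 7.5:1 reproduce to within about 1.3 percentage points.

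**Step 4: what one decision can move.** The documents do not say how many stratification errors to expect, so the unit here is one patient. The simulation fits a linear model at a single time point with treatment and stratum. It uses 22/11 TNFi-naive and 8/4 TNFi-failure patients (33 and 12 split 2:1), SD 45, a treatment difference of 42, and 300 simulated trials per setting. The stratum effect is an assumption, set at 0, 20 or 40 points. Entries are absolute shifts in the estimated difference, in points.

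| Action | Stratum effect 0 | 20 | 40 |
|---|---|---|---|
| Reclassify one patient, average | 0.50 | 0.92 | 1.55 |
| Reclassify one, most influential patient | 1.30 | 1.93 | 2.95 |
| Reclassify three patients, average | 0.76 | 1.18 | 1.99 |
| Exclude one patient, average | 1.65 | 1.66 | 1.67 |
| Exclude one, most influential patient | 6.48 | 6.43 | 6.45 |

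The rows for the most influential patient are averages of the largest shift in each simulated trial, not hard upper limits.

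A hand check agrees in order of magnitude. Removing a placebo patient who lies d points from the mean of the other 14 moves the placebo mean by d/15: 45/15 = 3.0 for one SD and 90/15 = 6.0 for two. For spesolimab, d/30 gives 1.5 and 3.0.

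**Step 5: relative size.** Against the SE of 14.23, an average exclusion is 1.7/14.2 = 0.12 SE and the most influential one is 6.5/14.2 = 0.46 SE. An average reclassification is 0.5/14.2 to 1.6/14.2, or 0.04 to 0.11 SE.

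**The case against.** Several points on the other side have force.

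- **The covariate.** A reader might infer that the C3.02 review settles the stratum value in the primary model. No passage says so. Protocol 7.2.2 says which stratum counts, but not when or by whom it is fixed, and SAP 7.4.1 only lists the term. The link is a reasonable inference and no more.
- **Room for judgement.** A reader might picture an open clinical decision on whether a past TNFi course failed. Inclusion criterion 5 admits only biologic-naive or TNFi-failure patients. A TNFi-treated patient who did not fail is an eligibility deviation under A1.04, which is not deferred. Protocol 3.1 defines primary and secondary failure. For eligible patients the check is therefore largely prior TNFi use, yes or no, although some judgement remains.
- **The sizing margin.** It is tempting to set the PPS shifts against the 12 points between the assumed 42 and the 30-point criterion. That margin belongs to the primary estimate on all treated patients, which a C3.02 exclusion does not touch.
- **Protocol 7.2.1.** Its deadline is tied to the final analysis, which could look like a second gap if the team is already unblinded at the primary analysis. The tighter wording of SAP 6.2 and 6.3 largely closes it.
- **Safeguards and stakes.** SAP 8 requires changes to data up to EoT after treatment release to be documented and summarised in the CTR. SAP 7.4.2 says only that the PPS analysis may be done, although SAP 6.3 says that the PPS will be used. No confirmatory test is planned.

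These points limit the size of the problem. They do not remove the conflict between the C3.02 comment and the general rules. The SAP 8 safeguard also concerns changes to trial data and is not a rule for making deviation decisions blind.

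**Conclusion.** The inconsistency is real: a PPS exclusion that can be judged blinded is scheduled after the deadline set by SAP 6.2 and 6.3, with no reason given and no protected blinded interval before treatment release. The documents do not say that the reviewers will be unblinded, only that treatment can be known by then. Nor do they show that any stratification error has occurred.

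The effect is modest. One exclusion typically moves the estimated difference by about 1.7 points, and one reclassification by 0.5 to 1.6 points, against an SE of 14.2. These figures rest on the protocol's SD and arm sizes, on assumed stratum effects of 0 to 40 points, and on a single-time-point simplification of the MMRM. The main loss is in the credibility of the PPS sensitivity analysis. Any effect on the primary model is indirect and inferred. The sample size of 45 and the 80.1% are unaffected.

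**What to change.** - In SAP Table 6.2:1, replace the C3.02 comment with a programmed check of IRT stratum against eCRF TNFi history, followed by blinded manual review completed at or before the RPM/DBLM that precedes the first unblinding. If the analyses are separate, that is the primary-analysis lock.
- Freeze the corrected stratum variable at the same meeting, and say that this is the value used in the analyses. That turns the inferred link to the primary model into a stated rule.
- Keep judgement after lock only for the part of C2.01 that needs the treatment code.

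The cost is a change of SAP wording and one blinded listing before lock. It needs no new data and does not affect patients or the sample size.

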6.3 SUBJECT SETS ANALYSED

The following analysis sets will be defined for this trial:

Enrolled Set (ES)

This patient set includes all patients who signed informed consent. It will be used for analyses of patient disposition.

Randomized Set (RS):

This patient set includes all randomized patients. Treatment assignment will be as randomized.

Safety Analysis Set (SAF):

This patient set includes all patients who were randomized and received at least one dose of study drug. This is the main analysis set for efficacy and safety. Patients will be analyzed according to the actual treatment received.

Per-Protocol Set (PPS):

This patient set includes all patients in the randomized set who adhered to the CTP without any iPDs which are flagged for exclusion from the PPS in the table above. The PPS will be used for sensitivity analysis on the primary endpoint.

The discussion of all exceptional cases and problems and the decisions on the allocation of patients to populations will be made at latest at the RPM/DBLM.

Handling of Treatment Misallocations in Analysis Sets

If a patient is randomized but not treated, they will not be reported under their randomized treatment group for efficacy and safety analysis according to PPS, and SAF.

If a subject is treated but not randomized, they will be excluded from the efficacy analysis and safety analysis by definition. However, subjects under such circumstances will be described in the final clinical trial report.

If a subject is randomized but takes incorrect treatment during the study, then:

- For efficacy and safety analyses using the SAF which are based on actual treatment:
 - If a subject is planned to receive administration of Spesolimab (randomized to Speso), then they will be reported under the Spesolimab group if the subject receives at least 1 vial of randomized Spesolimab.
 - If a subject is planned to receive placebo treatment, then they will be reported under the placebo arm if they are treated and receive no vial of randomized Spesolimab. If the subject receives ≥ 1 vial of randomized Spesolimab, then the patient will be handled differently for efficacy analysis and safety analysis. It will keep as placebo for efficacy reporting. For safety, then the patient will be reported as treated with Spesolimab treatment group.

Proprietary confidential information © 2021 Boehringer Ingelheim International GmbH or one or more of its affiliated companies

Table 6.3: 1 Overview of use of patient analysis sets by class of endpoint and handling of estimand and missing data

Class of Endpoints	ES	RS	SAF	PKS	PPS
Disposition	OR	OR			
Compliance and exposure			OR		
iPD		OR			
Demographic/baseline characteristics		OR	OR		
Concomitant medication		OR			
Primary endpoint			EC-H-MMRM EC-H-MMRM ¹ EC-H-MMRM ⁴ EC-S-MMRM ¹ OC ² , OC-IR ²		EC-H-MMRM ¹
Secondary binary efficacy endpoints			EC-H-NRI, EC-H-NRI ¹ EC-H-NRI ⁴ OC ² EC-H-MI ³		
Secondary continuous efficacy endpoints			EC-H-MMRM EC-H-MMRM ¹ EC-H-MMRM ⁴ EC-S-MMRM ³ OC ²		
Further efficacy endpoints			Binary: EC-H-NRI Continuous: EC-H-MMRM ¹ All: OC ² ,		
Concentration & ADA			OR	OR	
Safety data			OR OC-IR		

¹ sensitivity/further analysis

² descriptive display only

³ selected endpoints.

⁴ subgroup analysis

For explanation of the different approaches with regard to missing data see [Section 6.6](#).

[figure not shown]
EC-H: Hybrid strategy by implementing estimand concept. Any data post rescue medication use will be censored.

EC-S: Supplementary strategy by implementing estimand concept. Any data collected after use of any rescue therapy or restricted medication are censored.

OC = observed cases excluding values after any use of rescue medication.

OC-IR = observed cases including also values after any use of rescue medication.

OR = original results.

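### Both documents assign the main efficacy set by actual treatment, while the SAP's own misallocation rule keeps a placebo patient given spesolimab in placebo for efficacy and leaves one case uncovered

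*SAP*

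**What the plan says.** Protocol 7.2.1 makes the Treated Set (randomised, at least one dose) the main set for efficacy and safety and adds, without exception: "Patients will be analyzed according to the actual treatment". SAP 6.3 defines the same population as the Safety Analysis Set (SAF). It says "This is the main analysis set for efficacy and safety" and gives the assignment rule: "Patients will be analyzed according to the actual treatment received".

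The SAP's misallocation rules open with "For efficacy and safety analyses using the SAF which are based on actual treatment". Under that heading there are two rules:

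- Randomised to spesolimab: "they will be reported under the Spesolimab group if the subject receives at least 1 vial of randomized Spesolimab". Nothing is said about a patient who receives no active vial.
- Randomised to placebo, with at least one active vial. For efficacy: "It will keep as placebo for efficacy reporting". For safety: "For safety, then the patient will be reported as treated with Spesolimab treatment group".

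Only the Randomized Set (RS) carries the rule "Treatment assignment will be as randomized". SAP Table 6.3:1 places the primary endpoint on the SAF, with the Per-Protocol Set (PPS) for sensitivity, and lists no efficacy endpoint on the RS.

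**The concern.** The general sentence and the heading say that efficacy is as treated. The placebo rule under that heading is as randomised. Two analysts could put the same patient in different arms of the primary comparison, and each could cite the SAP.

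Assignment by treatment received gives up the protection of randomisation for any patient it moves, because the reason for the error may be related to prognosis or site. With 15 patients planned on placebo, a single patient carries visible weight.

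Timing adds to this. SAP Table 6.2:1, deviation C2.01 (incorrect medication before Week 12), notes that it can be finally judged only after database lock, because unblinding information is needed. Who received what is thus settled with the codes known, and a choice between two conflicting sentences could be made at that point too.

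**Working it through.** **The rules case by case, for efficacy**

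| Randomised to | Received | General sentence (both documents) | Specific SAP rule |
|---|---|---|---|
| Spesolimab | at least 1 active vial | not clear if mixed | spesolimab |
| Spesolimab | no active vial | placebo, by implication | none |
| Placebo | no active vial | placebo | placebo |
| Placebo | at least 1 active vial | spesolimab, or not clear if mixed | placebo |

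The three cases with a specific rule all stay in the randomised arm. The conflict is in the last row and the gap in the second.

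**Backstop.** Table 6.3:1 has no efficacy analysis on the RS. The PPS excludes patients with incorrect medication (C2.01), so it drops them and does not analyse them as randomised. Protocol 4.2.1 mentions an ITT analysis, but neither 7.2.1 nor SAP 6.3 defines such a set.

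**Vials.** The rules count vials, but maintenance doses come in pre-filled syringes (protocol 4.1.1 and 6.2.2). Read literally, a placebo patient given active drug only by syringe stays in placebo even for safety. A spesolimab patient given wrong infusions but correct syringes falls into the uncovered case.

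**The plan's own figure.** Inputs: 30 and 15 patients (protocol synopsis); SD 45 points, and a threshold of a 30-point observed difference (7.5); true changes of -62% and -20%, a difference of 42 (Table 7.5:1).

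- SE = 45 × √(1/30 + 1/15) = 14.23.
- P(difference ≥ 30) = Φ((42 − 30)/14.23) = 80.0%, against the stated 80.1%.
- A gamma simulation (100 plus the percent change, SD 45, 100,000 runs) also gives 80.0%. The gamma shift is an assumption, since the parameters are not given. All 11 rows of the table reproduce within 2 points by both methods.

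**Effect of the rule.** The documents give no misallocation rate. Assumed: m = 1 to 3 misallocated patients, errors unrelated to outcome, and SD held at 45.

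For m = 1:

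- Placebo patient given fully effective drug, kept in placebo: placebo mean = (14 × (−20) + (−62))/15 = −22.8, so the difference is 62 − 22.8 = 39.2. Moved to spesolimab, the difference stays 42.0 with 31 and 14 patients.
- The same patient if the stray drug has no effect: kept in placebo, 42.0. Moved, 42 × 30/31 = 40.6.
- Spesolimab patient given no active drug, as randomised: active mean = (29 × (−62) + (−20))/30 = −60.6, so the difference is 40.6. As treated, it is 42.0 with 29 and 16 patients.

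| Case | Rule | Expected difference, m = 1 / 2 / 3 | P(≥ 30 points), % |
|---|---|---|---|
| Placebo patient, full drug effect | kept in placebo | 39.2 / 36.4 / 33.6 | 74.1 / 67.4 / 60.0 |
| | moved | 42.0 throughout | 79.6 / 79.1 / 78.6 |
| Placebo patient, no drug effect | kept in placebo | 42.0 throughout | 80.0 throughout |
| | moved | 40.6 / 39.4 / 38.2 | 76.9 / 73.7 / 70.5 |
| Spesolimab patient, no active drug | as treated | 42.0 throughout | 80.4 / 80.7 / 81.0 |
| | as randomised | 40.6 / 39.2 / 37.8 | 77.2 / 74.1 / 70.8 |

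**The case against.** The SAP says expressly that the misallocated placebo patient is handled differently for efficacy and for safety. A specific exception normally overrides a general sentence, and the SAP exists to add detail to the protocol. SAP section 4 is blacked out, so a declared departure from the protocol cannot be ruled out. SAP 6.3 also refers exceptional cases to the report planning or database lock meeting.

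The uncovered case is remote. A patient who completes treatment would need the wrong product at three infusions and at four visits of four syringes each. Vials and syringes have individual numbers assigned by IRT (protocol 4.1.3), a two-person check applies (4.1.4), and plasma concentrations give a further check on compliance (4.3). Patients with incorrect medication are flagged and left out of the PPS, so their influence can be seen.

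Much of this stands, and it sets the priority. The exception is probably what an analyst would follow, and misallocation may never happen. Three things remain. The heading directly above the exception still says that efficacy is by actual treatment. The protocol has no exception. The meeting cannot fully settle a deviation that needs unblinded information. On a literal count of vials, wrong product at the infusions alone would also be enough to reach the uncovered case.

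**Conclusion.** The conflict and the gap are real, in the rule that governs the primary comparison, and the priority is low. One misallocated placebo patient given fully effective drug changes the expected difference by 42.0 − 39.2 = 2.8 points, depending on the sentence followed. One spesolimab patient given no active drug changes it by 42.0 − 40.6 = 1.4 points. Both are small against a standard error of 14.23, in a trial with no confirmatory test (protocol 7.1). They rest on the planning values, an assumed number of errors, and errors unrelated to outcome.

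A reader might infer three stronger things that the documents do not support:

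- That the plan breaks randomisation for misallocated patients in general. The specific SAP rules keep every covered case in its randomised arm for efficacy.
- That the SAP moves untreated spesolimab patients to placebo, making the rule one-sided. No sentence says so; the move is only implied by the general definition.
- That the shift in the active mean from −62% to −60.6% measures bias under the plan. It is dilution under as-randomised assignment. Under the assumptions above, the as-treated difference stays at 42.0.

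The case for as-randomised assignment is comparability and a rule fixed before unblinding, not a larger estimate.

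**What to change.** In protocol 7.2.1 and SAP 6.3, state that efficacy in the Treated Set/SAF is analysed by randomised treatment in all cases, including a spesolimab-randomised patient who received no active drug. Limit assignment by actual treatment to safety. Correct the misallocation heading to match, and drop the vial-based rule for efficacy. For safety, count pre-filled syringes as well as vials. Make the change before treatment codes are released.

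The cost is wording only: no new data, and for efficacy no change in any case that the specific SAP rules already cover. The downside is a small dilution if a spesolimab-randomised patient received no active drug, 1.4 points for one such patient at the planning values.
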